6.2 FIDELITY

No text is to be entered in this section; rather it should be included under the relevant subheadings below. This section refers to efforts made to confirm that the intervention is appropriately conducted by the

*interventionist(s). It is distinct from the content of **Section 6.4, Study Intervention Adherence**, which is intended to capture a study participant's adherence to an intervention.*

6.2.1 INTERVENTIONIST TRAINING AND TRACKING

The intervention is conducted entirely by the curriculum hosted on the mobile web-app. Therefore, there is no additional fidelity checks required to ensure the interventionist is conducting the intervention as intended. However, the research staff do review the administrative dashboard to ensure the mobile web-app is functioning appropriately. All issues are noted and resolved within 24 hours.

6.3 MEASURES TO MINIMIZE BIAS: RANDOMIZATION AND BLINDING

Participants will be assigned to conditions by an algorithm programmed into the computer-based research portal. Randomization will utilize a permuted-blocks randomization scheme. Blocks of size 4 and 6 will be used. Assignments within blocks will be random but balanced among the two conditions and the order of the blocks (4 vs 6) also will be random. This procedure will ensure that the number of participants randomized to each condition will be equal, that any imbalance among the conditions at any point during the recruitment and randomization will be modest, and that it will be very difficult to guess the assignment of the next participant. Because the intervention and control materials are inherently different, participants and research staff cannot be blinded to assignment.

6.4 STUDY INTERVENTION/EXPERIMENTAL MANIPULATION ADHERENCE

Participants' adherence is tracked entirely through mobile website administration page. Participants are given full and immediate access to all 12 modules and mobile web tools. Adherence is assessed by module access (dichotomy), number of logins, number of pages visits, and number of minutes in each module and tool for the mobile web-app. Control-arm adherence (e.g., usual care) is not collected.

6.5 CONCOMITANT THERAPY

N/A

6.5.1 RESCUE THERAPY

N/A

7 STUDY INTERVENTION/EXPERIMENTAL MANIPULATION DISCONTINUATION AND PARTICIPANT DISCONTINUATION/WITHDRAWAL

No text is to be entered in this section; rather it should be included under the relevant subheadings below.

7.1 DISCONTINUATION OF STUDY INTERVENTION/EXPERIMENTAL MANIPULATION

When a subject discontinues from the intervention but not from the study, remaining study procedures will be completed as indicated by the study protocol. If a clinically significant finding is identified (including, but not limited to changes from baseline) after enrollment, the investigator or qualified designee will determine if any change in participant management is needed. Any new clinically relevant finding will be reported as an adverse event (AE). The data to be collected at the time of study intervention discontinuation will include the following: the reason(s) for discontinuing the participant from the intervention, and methods for determining the need to discontinue

7.2 PARTICIPANT DISCONTINUATION/WITHDRAWAL FROM THE STUDY

Participants are free to withdraw from participation in the study at any time upon request.

An investigator may discontinue a participant from the study for the following reasons:

- Lost-to-follow up; unable to contact subject
- Participant withdraws consent for further participation and/or data use.
- Safety concerns: any SAE or AE judged related to participation that warrants removal, per the Data and Safety Monitoring Plan and IRB reporting rules.
- Ineligibility discovered post-enrollment, duplicate enrollment, or other protocol violations that compromise data integrity.
- Investigator decision that continued participation poses undue burden or risk (e.g., credible threats of harm), consistent with IRB policies.

The reason for participant discontinuation or withdrawal from the study will be recorded on a dedicated Case Report Form (CRF). Participants who withdraw or are discontinued after randomization will not be replaced; enrollment continues until the target sample size is reached.

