9.3 POPULATIONS FOR ANALYSES

Because randomization carries the expectation of creating treatment groups equivalent with respect to known and unknown prognostic factors, removing randomized participants from the analysis runs the risk of tampering with this balance and introducing bias into the treatment comparisons. As a result, an intention-to-treat analytic approach will be followed such that all participants randomized into the study will be included in all analyses irrespective of protocol violations post randomization. Even with our best efforts, we can expect some missing data. For the primary outcome, missing data will be limited to cases where we are unable to receive a weight as per participant request. Because we allow participants to opt out of any biometric or question, there is the possibility that there is missing data for the primary outcome. However, very little missing data is anticipated. For secondary measures, missing data will consist of those who fail to complete the 3 or 6-month follow-up survey. We will conduct an initial evaluation of missingness by performing a series of logistic regression analyses where the indicator of missing data is the outcome and potential explanatory variables (e.g., condition, screening status, demographic characteristics) serve as predictors. We will then use imputation to manage missing data.

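### Section 7.2 lets unblinded staff take randomised participants out of the study for late-found ineligibility or violations, with no requirement to keep weighing them, which conflicts with Section 9.3

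*Combined protocol and SAP*

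**What the plan says.** Section 7.2 opens its list of grounds with "An investigator may discontinue a participant from the study for the following reasons". One ground is "Ineligibility discovered post-enrollment, duplicate enrollment, or other protocol violations that compromise data integrity". Another is "Safety concerns: any SAE or AE judged related to participation that warrants removal", tied to the monitoring plan and IRB rules. The list also covers loss to follow-up, withdrawal of consent, and an investigator's view that staying in would be too burdensome or risky. The section adds: "Participants who withdraw or are discontinued after randomization will not be replaced; enrollment continues until the target sample size is reached".

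Section 7.1 deals with a different case: "When a subject discontinues from the intervention but not from the study, remaining study procedures will be completed as indicated by the study protocol". Neither section says what happens to later weights once a participant has been discontinued from the study itself.

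Section 6.3 states: "Because the intervention and control materials are inherently different, participants and research staff cannot be blinded to assignment".

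Section 9.3 sets the analysis population: "all participants randomized into the study will be included in all analyses irrespective of protocol violations post randomization". On missing weights it says: "For the primary outcome, missing data will be limited to cases where we are unable to receive a weight as per participant request". It then plans imputation, without naming a method or the assumption behind it.

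**The concern.** The same event is treated in two ways. A violation found after randomisation must not affect inclusion under Section 9.3, but it may end study participation under Section 7.2. Section 7.1 secures follow-up only for people who stop the intervention alone, so nothing secures a 3- or 6-month weight for someone removed from the study. If Section 7.2 is used and visits stop, a primary outcome is lost that could have been observed.

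Two features make this more than untidy wording. First, the decision comes after randomisation and is made by people who know the arm, so the rate or reasons for removal can differ between arms. Second, removal may be related to outcome. Eligibility requires prediabetes according to a screener and no diabetes, A1C is measured at every visit, and the protocol does not say how a diabetes-range reading bears on eligibility. Section 8.2 also gives raised A1C needing a doctor's assessment as an example of an adverse event. People removed by such routes might well differ from the rest in weight change. That is the bias Section 9.3 gives as its reason for intention to treat.

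**Working it through.** **1. The plan's own figures, to see how much loss it can absorb.** Section 9.2 gives d = 0.43, alpha 0.05, power 0.80, a final sample of 136, 20% attrition and 164 randomised.

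- A two-sample t-test with equal arms and a one-sided 5% level needs 68 per arm, so 136 in total. This matches.
- 136 × 1.2 = 163.2, rounded up to 164. This matches.
- 164 × (1 − 0.20) = 131.2, which is below 136. Power at d = 0.43 is then 0.790 one-sided, or 0.686 for the two-tailed test in Section 9.4.2.

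The plan names a paired, two-tailed test, which does not give 136. That is a separate matter and is used here only to show that there is no slack beyond the 20%. The documents do not say whether removals under Section 7.2 are counted within it. If they came on top (assumed rates, complete cases only):

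| Extra removal | Weights observed | Power, one-sided | Power, two-sided |
|---|---|---|---|
| 2% | 127.9 | 0.780 | 0.675 |
| 5% | 123.0 | 0.766 | 0.657 |
| 10% | 114.8 | 0.741 | 0.627 |

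**2. The sections side by side.**

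- Stops the intervention, stays in the study: follow-up continues (7.1), analysed (9.3).
- Discontinued from the study for ineligibility or a violation: follow-up not stated (7.2), still to be analysed (9.3).
- Source of missing weights: participant refusal only (9.3). Discontinuation (7.2) and loss to follow-up (7.3) are left out, although Section 9.2 allows for 20% attrition, and 164 × 0.20 = 32.8 people.

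**3. What removal could do to an arm mean.** Let f be the fraction of an arm removed and Δ the amount by which those removed would have done worse than those kept. The mean for the whole arm is (1 − f) × kept mean + f × (kept mean − Δ) = kept mean − fΔ. A complete-case mean is therefore too favourable by fΔ.

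The documents give neither f nor Δ. Assume f = 3-10% and Δ = 2-4 percentage points:

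- low end: 0.03 × 2 = 0.06 points
- high end: 0.10 × 4 = 0.40 points

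With 164 / 2 = 82 per arm, 3-10% is 2.5 to 8.2 people. For scale only, 0.43 × 7.7 = 3.31 points, and 0.06-0.40 is 2-12% of that. The product combines an effect size from a meta-analysis with the SD of a different, 12-month study, so it is not an effect the plan states.

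The shift favours STEPS if such removals fall in the STEPS arm and works against it if they fall in the control arm. It cancels if f and Δ are the same in both.

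**The case against.** The other side has a good case on several points.

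- A reader might infer that Section 7.2 makes intention to treat unachievable. It does not. Section 9.3 keeps everyone randomised and plans imputation, and nothing in Section 7.2 drops a removed participant's data.
- A reader might infer that removal ends outcome collection. That is a reasonable inference from the contrast with Section 7.1, but no section states it. What stands is that collection is not required.
- A reader might infer that related events can arise only in the STEPS arm, because controls get the app after the study. The safety ground is wider than the app. Both arms complete questionnaires, do the A1C self-test and are told to wear a Fitbit, and Section 8.3.3.2 judges relatedness to study procedures as a whole.
- The grounds have limits. Violations must compromise data integrity, and eligibility is checked before enrolment, with a doctor's form for pending cases. Section 8.2 expects serious events to be rare.
- Late-found ineligibility mostly reflects baseline status, which randomisation should balance. Only its detection, or the decision to act on it, could differ by arm.
- The 20% attrition allowance may already cover these losses.

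These points limit the likely size of the problem. They do not reconcile Section 7.2 with Section 9.3, do not supply the missing follow-up rule, and do not make the sentence on missing weights correct.

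**Conclusion.** The concern holds in a limited form. Section 7.2 permits unblinded removal after randomisation for ineligibility or violations, and no section requires weight to be measured afterwards. Section 9.3 includes these people in the analysis but does not foresee their missing weights. Intention to treat is still possible. For them it would depend on an unspecified imputation, whose assumption could fail if removal is related to arm and outcome.

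The size of any bias cannot be derived from the documents. The 0.06-0.40 points are an illustration that assumes 3-10% removed from one arm only, 2-4 points worse outcomes in those removed, and a complete-case analysis. They are not an estimate. The point should be corrected because the loss is avoidable and the remedy is cheap, not because a large bias has been shown.

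**What to change.** - **Ineligibility found after randomisation, and protocol violations:** state that they are recorded with the reason but do not end study participation. Invite these participants to the existing 3- and 6-month weight visits and analyse them in the arm assigned. This concerns outcome collection and analysis, not whether anyone goes on using the app.
- **Duplicate enrolment:** keep the first randomisation only.
- **Loss to follow-up and withdrawal of consent:** leave as they are.
- **Safety and burden or risk grounds:** reconcile Sections 7.1, 7.2 and 9.3 on whether weight is still sought where the sponsor's own safety rules and the participant's consent allow. Those rules need no change for this purpose.
- **Section 9.3:** correct the sentence on missing weights so that it includes discontinuation and loss to follow-up.
- **Reporting:** give discontinuations by arm and reason. Section 7.2 already requires the reason on a case report form.

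Section 4.1 is partly in the past tense. If follow-up is already complete, the report by arm and reason can still be made, with a sensitivity analysis for those removed.

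The cost is a few sentences of protocol text and follow-up contact for a few participants at visits that already take place.

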7.3 LOST TO FOLLOW-UP

A participant will be considered lost to follow-up if he or she fails to respond for the 6-month follow-up call and study staff are unable to contact the participant after at least 3 attempts.

The following actions must be taken if a participant fails to respond for a required study appointment:

- The site will attempt to contact the participant, reschedule the missed baseline or follow-up appointment, counsel the participant on the importance of maintaining the assigned visit schedule and ascertain if the participant wishes to and/or should continue in the study

- Before a participant is deemed lost to follow-up, the investigator or designee will make every effort to regain contact with the participant (where possible, 3 telephone calls including to a secondary contact number). These contact attempts will be documented in the participant's study file.
- Should the participant continue to be unreachable, he or she will be considered to have withdrawn from the study with a primary reason of lost to follow-up.

8 STUDY ASSESSMENTS AND PROCEDURES

No text is to be entered in this section; rather it should be included under the relevant subheadings below.

8.1 ENDPOINT AND OTHER NON-SAFETY ASSESSMENTS

This individually randomized, remote trial evaluates a mobile, web app diabetes prevention program versus a usual care control. All study activities are conducted in person with a trained research coordinator. The research coordinator obtains only weight and instant A1C measures if participant has agreed to the measures, and the remaining data is collected via a participant initiated questionnaire.

Screening, eligibility, and enrollment

- **Eligibility confirmation window.** Up to 30 days prior to enrollment. Research coordinator assesses eligibility and pending eligibility (from physical activity readiness questionnaire). For those with pending eligibility, the research coordinator must receive a doctor's signed form allowing participation in physical activity for the study.
- **Consent.** Participants complete electronic informed consent.
- **Baseline survey.** Immediately post-consent, participants complete a baseline questionnaire.
- **Randomization.** After baseline completion, participants are assigned to intervention or control.

Interventions begin (initial administration conditions)

- **Intervention arm.** Participants are told to immediately wear their fit bit for one week to get baseline physical activity measure. One week post baseline visit, they are provided their username and password to login and commence the intervention.
- **Control arm.** Participants are told to immediately wear their fit bit for one week to get baseline physical activity measure. They are also told they are in the usual care group and will receive access to the intervention post-study.

Measures and assessments (non-safety)

Baseline (pre-randomization)

- Demographics and contact details (mobile number required for delivery).
- Diabetes knowledge questionnaire
- Health behavior questionnaire
- A1C and weight biometrics

During intervention (process/dose)

- The administrative platform will provide all utilization details including login, page numbers, minutes used, and additional utilization statistics. These are used for exposure/dose summaries and adherence monitoring (not safety).

Follow-up (primary outcome window)

- **Primary outcome ascertainment:** Weight measure is utilized for future calculation of percent weight loss.
- **Follow-up questionnaire:** Repeat weight measurement at each follow up visit is used for percent weight loss.

Outcome definitions (non-safety)

- **Percent weight loss:** Calculated between weight at three different time points. This is used to calculate a percent weight loss in the participant.
- **Exposure/dose metrics:** Number of modules completed; number of minutes in the intervention; and number of times interactive tools utilized.

Administration, scoring, and data quality

- **Administration.** All questionnaires are self-administered via computer or tablet.
- **Scoring.** Multi-item scales are scored per codebook (sum or mean of valid items; higher scores reflect greater endorsement or knowledge, as defined). Missing-data rules (e.g., minimum items required) are pre-specified.
- **Data capture.** Survey responses are time-stamped and stored on the study platform'

Qualified personnel

- **In person visit biometrics:** Conducted by trained study staff.

8.2 SAFETY ASSESSMENTS

The current study gathered two biometric data points: (1) weight and (2) A1C levels using a rapid at-home assessment. Given the A1C test, the study followed the following protocol.

A1C Protocol for Safety Assessment. There are some minor health risks associated with conducting and obtaining information from a rapid A1C test. The use of a rapid A1C test is no more of a risk than using a blood glucose meter. It does not require blood to be drawn, in large amounts, or using a syringe. It also does not require a medical professional to complete. An A1C self-check will be conducted by the participant after being provided with instructions by ISA Staff. ISA Staff will monitor to ensure the participant is following directions. This test requires a droplet of blood only slightly larger than a traditional glucose monitor test. Participants will do the step-by-step instructions and then show ISA Staff their A1C reading. If a participant does NOT want to participate in doing the test, they will not be required to. There are minimal risks associated with the test. To alleviate the risks, ISA Staff will implement the following procedures for the following associated risks.

First, even though ISA Staff will be instructing the participant to self-test, they will wear a new set of latex gloves with each reach in the case they need to assist the participant. They will also throw all supplies in a sharps container once the test is completed. They will disinfect the area where the test is conducted as well.

While the blood sample is just a droplet of blood, there might be participants who have anxiety about blood and/or may feel light-headed at the sight of blood. Therefore, all participants will be required to be seated while they conduct the self-test. Additionally, if a participant feels unwell due to the blood

droplet, ISA STAFF will immediately call CACOST Health Center Staff to come assess the participant. While highly unlikely, in the case that there is a medical emergency, ISA Staff will immediately contact first responders. After the incident has been handled and cleared, ISA Staff will immediately contact the PI to inform them of the event and will document details.

Additionally, there may be associated risks with the participant learning their A1C levels. If a participant's A1C level is in the diabetes range, they will be provided with a sheet with information on A1C levels and information about how to contact their primary care physician about their results. This sheet will provide CACOST Health Center contact information as well.

Further safety procedures consist of: (1) AE/SAE identification and follow-up; (2) monitoring for distress potentially triggered by educational content; (3) privacy/technology safeguards (e.g., wrong-number texting, shared phones). AEs are any unfavorable or unintended psychological or practical effect temporally associated with participation in the study's activities (videos, , surveys), whether or not considered related. Examples include: heightened anxiety/distress about diabetes risk, perceived breach of privacy (e.g., texts seen by others on a shared device), escalation of medical mistrust that prompts clinical concern, and elevated A1C measures that require further doctors assessments. SAEs would be rare in this context and are defined per IRB policy (e.g., death, life-threatening event, hospitalization) regardless of attribution.

8.3 ADVERSE EVENTS AND SERIOUS ADVERSE EVENTS

No text is to be entered in this section; rather it should be included under the relevant subheadings below.

8.3.1 DEFINITION OF ADVERSE EVENTS

An AE is defined as an event that is unexpected, related or possibly related to research participation, and suggests that the research places subjects or others at a greater risk of harm than was previously known or recognized.

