Physical Activity. There are some minor health risks associated with participating in physical activity via the STEPS program. To minimize risk, ISA has instituted several protocols to protect participants and reduce their risk related to physical activity. To begin, it is an eligibility criteria that participants must PASS the PAR-Q+ Physical activity screener AND if yielded from the screener, receive a doctor's note indicating that they are medically cleared to exercise. Additionally, once in the program, there are disclaimers in the physical activity modules that remind participants that if at any point they are questioning engaging in physical activity due to health or have concerns they will need to contact their primary care provider. Contact information for the CACOST Health Center will be included. If a participant reaches out to ISA Staff at any point to indicate injuries with physical activity, ISA Staff will advise to stop all physical activity until further discussed with their primary care provider. Further, ISA Staff will report to the PI and a report will be made.

A1c Test. There are some minor health risks associated with conducting and obtaining information from a rapid A1C test. The use of a rapid A1C test is no more of a risk than using a blood glucose meter. It does not require blood to be drawn, in large amounts, or using a syringe. It also does not require a medical professional to complete. An A1C self-check will be conducted by the participant after being provided with instructions by ISA Staff. ISA Staff will monitor to ensure the participant is following directions. This test requires a droplet of blood only slightly larger than a traditional glucose monitor test. Participants will do the step-by-step instructions and then show ISA Staff their A1C reading. If a participant does NOT want to participate in doing the test, they will not be required to. There are minimal risks associated with the test. To alleviate the risks, ISA Staff will implement the following procedures for the following associated risks.

First, even though ISA Staff will be instructing the participant to self-test, they will wear a new set of latex gloves with each reach in the case they need to assist the participant. They will also throw all supplies in a sharps container once the test is completed. They will disinfect the area where the test is conducted as well.

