8.3.4 TIME PERIOD AND FREQUENCY FOR EVENT ASSESSMENT AND FOLLOW-UP

The occurrence of an adverse event (AE) or serious adverse event (SAE) may come to the attention of study personnel during study appointments.

All AEs, not otherwise precluded per the protocol, will be captured on the appropriate case report form (CRF). Information to be collected includes event description, time of onset, assessment of severity,

relationship to study procedures (assessed only by those with the training and authority to make a diagnosis), and time of resolution/stabilization of the event. All AEs occurring while on study will be documented appropriately regardless of relationship. All AEs will be followed to adequate resolution.

Any medical or psychiatric condition that is present at the time that the participant is screened will be considered as baseline and not reported as an AE. However, if the study participant's condition deteriorates at any time during the study, it will be recorded as an AE.

Changes in the severity of an AE will be documented to allow an assessment of the duration of the event at each level of severity to be performed. Documentation of onset and duration of each episode will be maintained for AEs characterized as intermittent.

The study coordinator will record events with start dates occurring any time after informed consent is obtained until 7 (for non-serious AEs) or 30 days (for SAEs) after the last day of study participation. At each study visit, the investigator will inquire about the occurrence of AE/SAEs since the last visit. Events will be followed for outcome information until resolution or stabilization.

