8.4.1 DEFINITION OF UNANTICIPATED PROBLEMS

This protocol uses the definition of Unanticipated Problems as defined by the Office for Human Research Protections (OHRP). OHRP considers unanticipated problems involving risks to participants or others to include, in general, any incident, experience, or outcome that meets all of the following criteria:

- Unexpected in terms of nature, severity, or frequency given (a) the research procedures that are described in the protocol-related documents, such as the Institutional Review Board (IRB)-approved research protocol and informed consent document; and (b) the characteristics of the participant population being studied;
- Related or possibly related to participation in the research (“possibly related” means there is a reasonable possibility that the incident, experience, or outcome may have been caused by the procedures involved in the research); and
- Suggests that the research places participants or others at a greater risk of harm (including physical, psychological, economic, or social harm) than was previously known or recognized.

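### Section 8.3.1 defines an adverse event by the unanticipated-problem test and contradicts six other sections, so expected or unrelated non-serious events may go unrecorded as AEs

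*Combined protocol and SAP*

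**What the plan says.** Section 8.3.1 sets three conditions joined by a final and. The first two are in "An AE is defined as an event that is unexpected, related or possibly related to research participation"; the third is that the event "suggests that the research places subjects or others at a greater risk of harm than was previously known or recognized". Section 8.4.1 defines an unanticipated problem as "any incident, experience, or outcome that meets all of the following criteria" and then lists the same three.

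Section 8.2 has a different definition: "AEs are any unfavorable or unintended psychological or practical effect temporally associated with participation". It adds that relatedness is not required, and its examples include distress about diabetes risk and raised A1C needing a doctor's assessment. Section 8.3.3.2 allows an AE to be graded not related, and 8.3.3.3 has each AE classed as expected or unexpected. Section 8.3.4 states: "All AEs occurring while on study will be documented appropriately regardless of relationship". Sections 8.3.5 and 8.3.6 require any AE, related to the intervention or not, to reach the IRB, within 72 hours if it is not serious.

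Section 2.3.1 says: "There are some minor health risks associated with participating in physical activity via the STEPS program". Section 6.3 says that participants and research staff cannot be blinded. Section 9.4.4, on safety analyses, reads N/A.

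**The concern.** A definition decides what enters the record; classification and reporting rules act only on what has entered. If the entry rule requires an event to be both unexpected and related, the expected and not-related classes in 8.3.3 have nothing to hold, and an instruction to document AEs regardless of relationship has no unrelated AEs to act on. A coordinator who follows 8.3.1 and one who follows 8.2 or 8.3.4 would build different safety datasets from the same participants.

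Two things are at stake. One is complete capture and IRB reporting of ordinary, non-serious harms, including those from physical activity, which the protocol itself lists as a risk. The other is whether harms can be compared fairly between arms in an open-label trial in which only one arm is given an activity programme during the study.

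**Working it through.** No arithmetic applies: the plan gives no event rate, and the point depends on none. The check sets the texts side by side.

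**Step 1. Compare 8.3.1 with 8.4.1.**

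| Criterion | 8.3.1 (AE) | 8.4.1 (unanticipated problem) |
|---|---|---|
| Expectedness | must be unexpected | "Unexpected in terms of nature, severity, or frequency given" the protocol documents and the population |
| Relatedness | related or possibly related | related or possibly related |
| Risk | greater than was known | "Suggests that the research places participants or others at a greater risk of harm" than was known |

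All three criteria match, and both definitions require all of them. Under 8.3.1, a non-serious AE and a non-serious unanticipated problem are the same thing. Section 8.4.2 nevertheless sets up a separate reporting stream for unanticipated problems, with the same 72-hour limit.

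**Step 2. Compare 8.3.1 with the sections that use the term AE.**

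- 8.2: relatedness not required. Conflicts with the second criterion.
- 8.3.3.2: has a not-related grade, which 8.3.1 leaves empty. Its related grade also covers events known to occur with study procedures, which sits badly with the first criterion.
- 8.3.3.3: an AE may be expected. Conflicts with the first criterion.
- 8.3.4: document regardless of relationship. Conflicts with the second criterion.
- 8.3.5 and 8.3.6: report whether or not related. These conflict with the second criterion, though least sharply, because they refer to the intervention, whereas 8.3.1 refers to research participation more broadly.

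**Step 3. Run typical events through the rules.** Section 8.3.3.3 calls an event unexpected when its nature, severity or frequency departs from the described risks.

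| Event | AE under 8.3.1? | AE under 8.2? | Other route |
|---|---|---|---|
| Minor exercise injury of the kind foreseen in 2.3.1 | No, expected | Unclear, because it is physical | 2.3.1: report to the PI if the participant tells staff |
| Distress about diabetes risk, as foreseen in 2.3.1 | No, expected | Yes, a listed example | Visit inquiry in 8.3.4 |
| A1C in the diabetes range, as foreseen in 2.3.1 | No, expected | Yes, if it needs a doctor's assessment | 7.1: new clinically relevant findings are AEs |
| Minor illness judged unrelated (reviewer's example) | No, unrelated | Unclear, because it is physical | 8.3.4: document regardless of relationship |
| Hospitalisation | Not needed | SAE whatever the attribution | 8.3.2, with no filter |

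Two of the protocol's own examples of AEs in 8.2 thus fail its formal definition when they occur as 2.3.1 describes. The minor exercise injury is not clearly an AE under either definition.

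**Step 4. Effect on the comparison between arms.** Control participants receive usual care, so few study procedures exist to which an event could be attributed. Take the same unusually severe exercise injury in each arm. In the intervention arm it could be judged related and unexpected, and so could be an AE under 8.3.1 if it also suggested greater risk. In the control arm it would probably be judged unrelated and would not count. The entry rule itself then depends on the arm, and the judgement is made by people who know the assignment.

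**The case against.** The strongest reply is that 8.3.1 is a drafting slip and that the operational text around it points the other way. Much of this stands.

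- Section 8.3.4 has the investigator ask about AEs at every visit, treats deterioration of a pre-existing condition as an AE without any filter, and leaves judgement of relationship to people qualified to diagnose. The schedule of activities in 1.3 places AE reporting at all three appointments and between them, with no distinction by arm.
- Section 7.1 reports new clinically relevant findings as AEs, 2.3.1 provides for a report of activity injuries, and SAEs are defined without reference to relatedness or expectedness.
- Section 10.1.6 has the PI review AEs weekly.

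These routes are incomplete. The main recording rule and the visit inquiry in 8.3.4 act on whatever staff take an AE to be. The finding rule in 7.1 sits under discontinuation of the intervention. The injury report in 2.3.1 depends on the participant making contact and names no AE form.

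A reader might infer three stronger things that the documents do not support. The first is that expected or unrelated events would certainly go unrecorded; the routes above rule that out. The second is that 8.2 excludes all physical events; its raised-A1C example and the severity grades in 8.3.3.1, which mention systemic drug therapy, show that the wording is loose and does not cleanly exclude them. The third is that every exercise injury is expected; 2.3.1 describes minor risks only, so a more severe injury could be unexpected under 8.3.3.3.

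It is also fair to say that a comparison of harms is not among the stated objectives.

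**Conclusion.** The contradiction is certain: 8.3.1 matches the unanticipated-problem test on three of three criteria and disagrees with six other sections. The consequence is conditional. Non-serious events that are expected or judged unrelated may be missed as AEs, and so not reported to the IRB as AEs, if staff follow 8.3.1. Serious events are not affected.

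How many events this involves cannot be estimated from the documents. To say that 8.3.1 excludes all expected and all unrelated non-serious events only restates the definition and is not a measure of loss. The possible distortion between arms assumes that relatedness is judged with knowledge of assignment, which 6.3 makes likely, and that it is judged before an event is logged, which 8.3.1 implies and 8.3.4 does not. With 9.4.4 at N/A, no planned table by arm would reveal uneven capture. The primary and secondary efficacy analyses are untouched. The point should be corrected, but it does not threaten the trial's main conclusion.

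**What to change.** 1. Reconcile 8.2, 8.3.1 and 8.3.3 to 8.3.6 to a single AE definition: any untoward physical, psychological or practical occurrence after consent, whether or not related or expected.
2. Record relatedness and expectedness as attributes after the event has been logged. The classes in 8.3.3 then work as written.
3. Keep the three-part test in 8.4.1 only.
4. Apply the existing visit inquiry of 8.3.4 to both arms under that definition, and state that activity injuries reported under 2.3.1 go on the AE form.
5. Replace N/A in 9.4.4 with descriptive AE and SAE counts by arm.

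The cost is protocol wording, one extra table, and slightly more AE forms. There will also be somewhat more IRB reports, because 8.3.5 sends every AE to the IRB. Treatment, sample size and the efficacy analyses do not change.
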